Endpoints	
Primary Endpoints
 
 Completion of 5 vascular and 4 infectious disease care processes, modeled as percent indicated and dichotomously (all relevant completed vs. missing ≥ 1) Development and refinement of recruitment and retention strategies that meet our goal targets of 60% and 80%, respectively 
Secondary Endpoints
 
 Amputation, either major or minor, within 3 months of follow-up

[figure not shown]
Study Design	This is a phase II pre-post serial cohort design trial with adaptive recruitment and retention strategies. Enrollment will be implemented in two phases; healthcare systems will be enrolled in consecutive 6-month periods.
Study Intervention	A rural integrated care model consisting of a care algorithm for use by rural primary care providers to guide integrated care for patients with diabetic foot ulcers, and a referral checklist for use by rural schedulers to place referrals with urban specialists.
Total Number of Subjects	Up to 45 patient participants will be enrolled in the study with additional historical control patients obtained via chart review (1 active patient participant; 5 historical control patients, up to 180 patients total). Up to 30 healthcare workers will be enrolled (180+30=210 individuals participating in the care algorithm pilot). From the pool of patients and healthcare workers approached for recruitment, we will ask up to 36 individuals, consisting of 18 patient participants and 18 healthcare worker participants, to participate in feedback interviews; this group will be a mix of both those that enrolled in the integrated care intervention study and those that declined participation in the study. These individuals will provide qualitative data needed to build recruitment and retention strategies, meeting our second objective. We are uncertain of the exact mix of qualitative participants who will have consented or not to participate in the care algorithm pilot. Therefore, the total number of subjects is anticipated to be between 190 and 246, including historical controls.
Study Population	Patient participants are adults aged 18+ diagnosed with diabetic foot ulcers and receiving care at a participating clinic. Health workers include primary care providers, other healthcare providers such as specialists, and schedulers employed at a participating clinic.

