6.0 STUDY OBJECTIVES AND ENDPOINTS

Objectives	Endpoints
Primary	

Evaluate the potential of our integrated care model to reduce major amputations by examining its impact on guideline-concordant care processes, including urban specialty referral	A) Completion of 5 vascular and 4 infectious disease care processes, modeled as percent indicated and dichotomously (all relevant completed vs. missing ≥ 1) B) Amputation, either major or minor, within 3-month follow-up
Build recruitment and retention strategies for the trial that work across diverse, rural clinics	Development and refinement of recruitment and retention strategies that meet our goal targets of 60% and 80%, respectively

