8.6 Early Termination and Withdrawal

All subjects are free to withdraw from participation in the study at any time upon request via letter as described on the consent form.

The Principal Investigator (PI) may discontinue or withdraw a healthcare worker from the study at her discretion for failure to consider use of the integrated care model with their patient participants, although deviation from the model will be allowed based upon the rural provider's clinical judgement.

Patient participants who sign the informed consent form, receive the study intervention, then subsequently withdraw, or are withdrawn or discontinued from the study will not be replaced.

The following actions will be taken if a patient participant withdraws or fails to return the three month follow-up phone call:

- Before a patient participant is deemed lost to follow-up, the investigator or designee will make every effort to regain contact with the participant where possible, by completing up to 3 telephone calls. These contact attempts shall be documented in the participant's study file. Participants that do not agree to participate in the follow-up phone call will be asked to provide a reason for discontinuing participation.
- If the patient participant continues to be unreachable, they will be considered to have withdrawn from the study with a primary reason of lost to follow-up. The withdrawn date is the last day of attempted contact.

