11.2 Recruitment and Retention Data Collection (Quantitative Data Collection)

We will use recruitment and retention data to assess the impact of the initial strategies and subsequent adaptations. We will keep logs of participant recruitment and retention. For healthcare worker (rural providers and schedulers) recruitment, we will record how many healthcare workers at each site: 1) were emailed an invitation to the recruitment meeting, 2) met with the study PI or research coordinator, and 3) consented to participate. Retention for healthcare workers will be defined as not having withdrawn consent to participate in the study and will not be based on their use of the integrated care model, since deviation from the model will be allowed if it is in the best interest of the patients as determined by the participating rural provider. Retention for administrators and other staff not formally consented in the quantitative portion will be defined as willingness of the clinic to continue to support the research endeavors.

For patient participant recruitment, we will record the number of patients who: 1) were contacted by phone, 2) completed the face-to-face appointment, and 3) consented to participate. For patient participant retention, we will log how many patient participants withdrew from the study or were lost to follow up before the 3-month telephone call. Logs will separate data into three distinct groups corresponding to adaptive iterations of the recruitment and retention strategies.

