11.3.2 Quantitative Data Analysis

[name] will serve as the study's biostatistician and be available to assist with the quantitative data analysis. We will calculate recruitment and retention rates prior to activating the next clinic. We will compare results to our goals of 60% and 80%, respectively.^{34,35} We will create recruitment and retention cascade graphics for both healthcare workers and patients to assist with determining which steps in the process have the highest attrition. Subsequent adaptations will focus on these steps. We will use descriptive statistics, such as counts, rates, and percentages, to summarize recruitment and retention during each cycle of adaptation. The denominator for healthcare worker recruitment steps will be the number of healthcare workers emailed to attend an informational meeting. The denominator for healthcare worker retention will be the number enrolled in the study. Retention will be assessed every 3 months until the end of the study, varying across each clinic due to staggered activation. The denominator for patient recruitment will be the number of patients we attempted to contact by telephone. The denominator for patient retention, assessed at the 3-month follow-up telephone call, will be the number of patient participants enrolled in the study. Comparisons of recruitment and retention between adaptations will be performed using ANOVA or chi-square tests, depending on the outcome types for these endpoints. Also, correlative measures will be calculated when such methods are informative.

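### The healthcare-worker retention rate cannot register workers whom the PI removes or workers who leave the clinic

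*Combined protocol and SAP*

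**What the plan says.** Section 11.2 gives one test for healthcare workers: "Retention for healthcare workers will be defined as not having withdrawn consent to participate in the study". It adds that retention "will not be based on their use of the integrated care model, since deviation from the model will be allowed" when the provider judges this best for the patient. Section 11.3.2 sets the base and the timing: "The denominator for healthcare worker retention will be the number enrolled in the study", and "Retention will be assessed every 3 months until the end of the study". It also says "We will compare results to our goals of 60% and 80%, respectively", and plans recruitment and retention cascades for both workers and patients, with later adaptations aimed at the steps that lose most people.

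The targets appear in a primary endpoint in section 6.0: "Development and refinement of recruitment and retention strategies that meet our goal targets of 60% and 80%, respectively". The synopsis sets the size of the group: "Up to 30 healthcare workers will be enrolled".

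Section 8.6 provides an exit that the worker does not choose. The PI "may discontinue or withdraw a healthcare worker from the study at her discretion for failure to consider use of the integrated care model", although deviation on clinical judgement is permitted. Sections 8.6 and 12.4.8 describe a participant's own withdrawal as a written request. Section 8.1.1 lists employment at a participating clinic, and availability throughout the study, among the inclusion criteria. No section says how a worker who later leaves, or whom the PI removes, counts in the retention rate.

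**The concern.** There are at least three ways for an enrolled worker to stop taking part: withdrawing consent, being discontinued by the PI, and leaving the clinic. The retention rule sees only the first. The other two leave the person in both numerator and denominator, so the rate does not move however often they occur.

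The patient rule in the same section is wider. It logs withdrawal and loss to follow-up, and section 8.6 treats an unreachable patient as withdrawn. Workers have no equivalent.

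What is at stake is the use made of the number. It is compared with the 80% goal, it feeds the cascade that directs adaptations, and it goes to the co-design session that prepares the statewide trial (section 11.4). Patients are eligible only if their own provider has enrolled (section 7.1), so the loss of a provider matters to how such a trial would run. A rate that cannot show those losses could make a retention strategy look better than it was.

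**Working it through.** **Figure to reproduce.** There is none. The documents give an 80% goal but no expected rate, sample size or power for healthcare-worker retention.

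**Step 1: apply the rule to each exit.**

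| Exit | Where described | Consent withdrawn? | Status under 11.2, read exactly |
|---|---|---|---|
| Worker withdraws in writing | 8.6, 12.4.8 | Yes | Not retained |
| PI discontinues the worker | 8.6 | No | Retained |
| Worker leaves the clinic and does not write | Not covered; employment is an entry criterion in 8.1.1 | No | Retained |

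**Step 2: write down the two rates.** Let N be workers enrolled, W consent withdrawals, D discontinuations by the PI and L departures without withdrawal, with nobody counted twice.

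- Rate as defined = (N − W)/N
- Active rate = (N − W − D − L)/N
- Difference = (D + L)/N

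With N = 30 (the maximum in the synopsis), each uncounted loss is worth 1/30 = 3.3 percentage points.

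**Step 3: illustrate.** The target is 0.80 × 30 = 24 retained. The documents give no values for D and L, so those below are assumptions, with W = 0.

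| D + L | Rate as defined | Active rate |
|---|---|---|
| 3 | 30/30 = 100% | 27/30 = 90.0% |
| 7 | 30/30 = 100% | 23/30 = 76.7% |
| 10 | 30/30 = 100% | 20/30 = 66.7% |

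Seven is the smallest number of losses that takes 30 workers below 80%. It was chosen for that reason and is not a forecast.

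**Step 4: can the rate as defined miss the target?** Yes, if 7 or more of 30 withdraw consent. Suppose each worker withdraws independently with probability w. Then P(meet) = P(X ≥ 24), where X is binomial with n = 30 and success probability 1 − w.

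| Assumed w | 2% | 5% | 10% | 15% | 20% | 25% |
|---|---|---|---|---|---|---|
| P(meet) | 1.000 | 0.999 | 0.974 | 0.847 | 0.607 | 0.348 |

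**Step 5: count the other losses too.** Replace 1 − w by 1 − w − l, where l is the assumed probability of PI discontinuation or departure.

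| Assumed l | 5% | 10% | 15% | 20% | 30% |
|---|---|---|---|---|---|
| w = 5%: as defined | 0.999 | 0.999 | 0.999 | 0.999 | 0.999 |
| w = 5%: stricter rule | 0.974 | 0.847 | 0.607 | 0.348 | 0.059 |
| w = 10%: as defined | 0.974 | 0.974 | 0.974 | 0.974 | 0.974 |
| w = 10%: stricter rule | 0.847 | 0.607 | 0.348 | 0.160 | 0.017 |

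The flat rows show the defect: under the rule as written, l has no effect. Every rate in steps 4 and 5 is an assumption.

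**The case against.** The strongest reply is that this is an unspecified edge case and not a wrong rule. Section 8.6 lets the PI discontinue or withdraw a worker, and the team might simply log a PI withdrawal as not retained. That is possible, but section 11.2 turns on the withdrawal of consent, and sections 8.6 and 12.4.8 make that the participant's step. Two analysts could report different rates from the same log, and the literal reading gives the higher one.

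A second reply is that leaving a job may have nothing to do with the study's retention strategies. This stands. It is a reason to show causes of loss separately, but not a reason to leave departures out of sight.

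A third is that the number carries limited weight. The endpoint concerns developing and refining strategies, section 11.3.1 places the targets in the later statewide trial, the 80% goal is not set separately for workers, and no pass/fail decision hangs on the worker rate. Weekly coordinator meetings (sections 8.5.1 and 10.1.2) and retention interviews (section 11.1.1.2) could also reveal turnover. These points reduce the consequence. They do not make the reported rate or the cascade correct, and section 11.3.2 compares retention with 80% in a paragraph that covers both groups.

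Three stronger readings are tempting and are not supported:

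- A reader might infer that the 80% target is met almost by definition. It is not. Consent withdrawals count, and step 4 gives a probability of 0.348 at an assumed 25% withdrawal.
- A reader might infer that the PI removes workers for not using the model, so that non-use ought to count as loss. The ground in 8.6 is not having considered the model. Section 11.2 leaves use out of retention deliberately and gives its reason.
- A reader might take section 8.3.2 to make continued employment a condition of staying in. It only describes how workers are identified, and section 8.1.1 states employment as an entry criterion.

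**Conclusion.** The concern holds in a limited form. Followed exactly, section 11.2 counts as retained any worker whom the PI discontinues under 8.6, and any worker who leaves the participating clinic without writing to withdraw. The rate set against 80% and the healthcare-worker cascade are blind to both.

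The overstatement is (D + L)/N. Its actual size cannot be known from the documents, which give no rates of turnover or PI removal. At 30 workers, 7 such losses would be enough to turn an active rate below target into a reported 100%. The conclusion rests on reading withdrawal of consent as the participant's own written act, as sections 8.6 and 12.4.8 describe it. It does not depend on the assumed rates, which only illustrate scale. It concerns the recruitment and retention objective and does not touch the care-process or amputation analyses.

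**What to change.** Amend section 11.2 so that, at each 3-month assessment, a healthcare worker is not retained if they have withdrawn consent, have been discontinued by the PI under 8.6, or are no longer employed at a participating clinic. Keep the provision that deviating from the model on clinical judgement does not count against retention. Report losses by reason, in the rate and in the cascade, so that job changes unrelated to the study can be told apart from disengagement.

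Patient enrolment has finished (section 13.2), so the team may already know some of these results. The consent-based rate should therefore stay and be reported beside the stricter one, with the amendment dated.

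The cost is about one sentence of text and one extra line in the report. The retention logs and the weekly meetings with workers should supply each worker's status. The downsides are that the stricter rate may be less favourable, and that it will include some departures that no retention strategy could have prevented.

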11.3 Recruitment and Retention Data Analysis

11.3.1 Qualitative Data Analysis

We will analyze interview transcripts using directed content analysis, where an existing conceptual model drives an *a priori* coding matrix.³⁶ The columns of the matrix will be composed of categories derived from the conceptual model.³⁰ Interview questions are placed in the matrix rows, with supporting quotes populating each cell. We will allow our matrix to be unconstrained.³⁷ This means that, while the majority of the coding matrix is predetermined, we will add new categories (columns) to reflect emerging facets of the data that may refute, extend, or enrich the conceptual model. We are using an unconstrained model because our intent is to capture all possible strategies to promote recruitment and retention.³⁶

Before coding begins, the PI and research coordinators will create a code book to define each category, tailoring definitions to rural recruitment and the current study. Core definitions will be based on those originally published.³⁰ The group will refine the code book iteratively using emerging data to hone *a priori* codes and define new ones relevant to emerging themes. Two study team members will code all transcripts independently (PI and a research coordinator). First, transcripts will be read for immersion. Second, portions of the transcripts pertaining to barriers and facilitators of recruitment and retention will be highlighted, regardless of whether they represent core concepts in the matrix. Starting analysis in this way prevents researchers from focusing too narrowly on *a priori* codes. Third, highlighted passages will be coded using the predetermined categories. Fourth, any highlighted text that fell outside the predetermined categories will be given a new code and entered into the unconstrained matrix.³⁶ Independent coders will meet to discuss discrepancies identified using NVivo comparisons of coded text and interpretations of code book definitions. If questions remain, [name] (qualitative co-investigator) will assist with resolution. Once the matrix is complete, researchers (Drs. [name] and [name]) will examine the data in each category and describe how the current process of recruitment is working, how recruitment strategies are impacted by different conditions, and interactions between different strategies.^{36,37} Analysis will be shared with the participating clinics and Rural Wisconsin Health Cooperative during a final co-design session to adapt recruitment and retention strategies to meet our target goals of 60% recruitment and 80% retention in a subsequent, wider state trial.

11.3.2 Quantitative Data Analysis

[name] will serve as the study's biostatistician and be available to assist with the quantitative data analysis. We will calculate recruitment and retention rates prior to activating the next clinic. We will compare results to our goals of 60% and 80%, respectively.^{34,35} We will create recruitment and retention cascade graphics for both healthcare workers and patients to assist with determining which steps in the process have the highest attrition. Subsequent adaptations will focus on these steps. We will use descriptive statistics, such as counts, rates, and percentages, to summarize recruitment and retention during each cycle of adaptation. The denominator for healthcare worker recruitment steps will be the number of healthcare workers emailed to attend an informational meeting. The denominator for healthcare worker retention will be the number enrolled in the study. Retention will be assessed every 3 months until the end of the study, varying across each clinic due to staggered activation. The denominator for patient recruitment will be the number of patients we attempted to contact by telephone. The denominator for patient retention, assessed at the 3-month follow-up telephone call, will be the number of patient participants enrolled in the study. Comparisons of recruitment and retention between adaptations will be performed using ANOVA or chi-square tests, depending on the outcome types for these endpoints. Also, correlative measures will be calculated when such methods are informative.

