5.4.2 Recruitment and Retention Strategies

Inadequate recruitment and retention into clinical trials are the two top reasons clinical trials fail.²⁷ Furthermore, rural participants are under-represented in clinical trials, and there is a paucity of data regarding how to improve rural participation.^{28,29} Therefore, it is critical that we develop strong recruitment and retention strategies during this pilot to assure subsequent trial success. We will collect quantitative data on the number of recruited patients and 3-month retention over the pilot. To improve these metrics, we will analyze qualitative data from healthcare workers and patients using an existing conceptual model of participant-centered recruitment and retention.³⁰ Our 2-wave, adaptive design allows us to pilot two iterations of recruitment and retention strategies. Adaptations will be co-designed with the Cooperative prior to activating the second and third clinics and upon completion of the pilot. Using qualitative data to drive improvements in recruitment and retention is a proven approach.^{31,32} In one instance, recruitment rates nearly doubled from 35% at the beginning of the pilot to 69% during the definitive trial.³¹⁻³³ Our goal is to develop strategies that achieve a recruitment rate of 60% and retention rate of 80%, which would place us in the top tertile of clinical trial performance and ensure an adequately powered statewide trial.^{34,35}

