13.2 Sample Size and Statistical Analysis

We have now finished enrolling active patients into the intervention. Our final number of active patients is 27. This is lower than our target enrollment of 45. Therefore, we re-calculated the number of historical controls needed to achieve adequate power for care processes. First we assume the probability of exposure among sampled control subjects is 0.6 and the correlation coefficient for exposure between matched cases and control subjects is 0.3. To detect an odds ratio of 0.26 versus the alternative of equal odds with 27 active patients and a matching sample of 5 historical controls per active patient (totaling 162 active and historical patients combined), and with a Type I error rate of 0.05, the power is 0.80706 (computed using PASS 2024, version 24.0.1).

When analyzing pilot data, descriptive statistics will be run on variables other than our primary and secondary outcomes. When analyzing our primary and secondary outcomes, we will stratify by clinic because they serve communities of differing socioeconomic status. Care processes will be modeled both dichotomously (all relevant completed vs. missing at least one) and continuously (as a percent of indicated care processes that occurred). In analyzing our primary outcome dichotomously, we will use a factorial experimental approach where the guideline-concordant and -discordant measures will be calculated. Additionally, due to the categorical nature of both our primary (dichotomously modeled care processes) and secondary (major and minor amputation) outcomes, we will build a multivariable Poisson regression model. When modeling guideline concordance care processes continuously, we use linear regression. In the primary analysis, we will require patients referred to a vascular or infectious disease specialist to be seen by that specialty, either in-person or via telemedicine, within 2 weeks per our algorithm. We will also conduct an intention-to-treat analysis where we include consults placed but not completed or delayed. Pre/post differences in completed referral rates, coupled with data on why a referral did not take place, will allow us to determine whether referral gaps would be best addressed by focusing on primary or specialty clinic processes.

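### Recruitment and retention are compared with the 60% and 80% primary-endpoint goals as point estimates without intervals; with 27 enrolled patients, retention that just reaches its goal is compatible with 62% to 94%

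*Combined protocol and SAP*

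**What the plan says.** The Synopsis and Section 6.0 list as a primary endpoint: "Development and refinement of recruitment and retention strategies that meet our goal targets of 60% and 80%, respectively". Section 5.4.2 gives the reason for the goals: reaching them would "ensure an adequately powered statewide trial".

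Section 11.3.2 holds the analysis. It calculates the rates and states: "We will compare results to our goals of 60% and 80%, respectively". The summary is descriptive: "We will use descriptive statistics, such as counts, rates, and percentages, to summarize recruitment and retention during each cycle of adaptation". The only tests named are between strategy versions: "Comparisons of recruitment and retention between adaptations will be performed using ANOVA or chi-square tests". No interval, required count or error rate is given for the comparison with 60% or 80%.

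The denominators differ by rate:
- **Patient retention:** "The denominator for patient retention, assessed at the 3-month follow-up telephone call, will be the number of patient participants enrolled in the study". Section 13.2 fixes that number: "Our final number of active patients is 27".
- **Patient recruitment:** patients whom the team tried to reach by telephone. The documents give no count.
- **Healthcare workers:** those emailed (recruitment) and those enrolled, up to 30 (retention).

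Section 11.2 logs patient retention through withdrawals and losses to follow-up before the 3-month call, and splits the logs into three groups by adaptation. Under Section 8.6, of patients who stay unreachable, "they will be considered to have withdrawn from the study with a primary reason of lost to follow-up". Section 10.2.3.2 and Appendix 10 record death from the chart. No section says how a known death enters the retention rate.

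**The concern.** An endpoint worded in terms of meeting numerical goals invites a conclusion of met or not met. With 27 patients, one patient more or fewer changes that conclusion, and a bare percentage does not show how little the data separate the two. The pilot's stated purpose is to prepare a statewide trial. A reader who sees 81.5% against a goal of 80% may take retention of that order as established, when the same data fit values some 18 points below the goal. Rates within single adaptation cycles rest on fewer patients still.

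**Working it through.** **The plan's own figure.** There is none to reproduce. The power statements in the Synopsis and Section 13.2 concern care processes only.

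**Inputs.** Goals of 60% and 80% (Section 6.0); 27 patients in the retention denominator (Sections 11.3.2 and 13.2); three log groups (Section 11.2); a planned eligible pool of 135 (Section 16.3), used only as an upper end for the unknown recruitment denominator.

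**Step 1: count needed for retention.** 0.80 × 27 = 21.6, so 22 retained reaches the goal (22/27 = 81.5%) and 21 does not (21/27 = 77.8%).

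**Step 2: exact 95% intervals.** The Clopper-Pearson lower limit solves P(X ≥ x | n, p) = 0.025 and the upper limit solves P(X ≤ x | n, p) = 0.025.
- 22/27: 61.9% to 93.7%
- 21/27: 57.7% to 91.4%

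The two intervals overlap almost entirely, although they fall on opposite sides of the goal.

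**Step 3: behaviour of the implied rule.** With X ~ Binomial(27, p), the goal is met if X ≥ 22.

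| True retention | Met | Missed |
|---|---|---|
| 60% | 1.5% | 98.5% |
| 65% | 5.1% | 94.9% |
| 70% | 13.6% | 86.4% |
| 75% | 29.9% | 70.1% |
| 80% | 53.9% | 46.1% |
| 85% | 79.0% | 21.0% |
| 90% | 95.3% | 4.7% |

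**Step 4: single cycles.** Cycle sizes are not given. An equal split is assumed: 27/3 = 9. Then 0.80 × 9 = 7.2, so 8 are needed; 8/9 has an interval of 51.8% to 99.7%, and the goal is met with probability 19.6% at a true 70%. With 15 in a cycle, 12 are needed; 12/15 has an interval of 51.9% to 95.7%, and the probability at a true 70% is 29.7%.

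**Step 5: patient recruitment.** The numerator is taken as 27. This is an assumption: enrolment requires more than consent (Section 10.2.2.3), so consents may exceed 27. Since 27/0.60 = 45, the overall goal is then reached only if 45 or fewer patients were attempted.

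| Attempted (assumed) | Rate | Exact 95% interval |
|---|---|---|
| 36 | 75% | 57.8% to 87.9% |
| 45 | 60% | 44.3% to 74.3% |
| 54 | 50% | 36.1% to 63.9% |
| 90 | 30% | 20.8% to 40.6% |
| 135 | 20% | 13.6% to 27.7% |

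**Step 6: healthcare workers.** At the maximum of 30 enrolled, 24/30 (80%) has an interval of 61.4% to 92.3%.

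**Step 7: deaths.** One patient is 1/27 = 3.7 points. Section 10.3.1 cites about 20% one-year mortality in a national cohort. At a constant hazard (assumption), 3-month mortality is 1 − 0.80^(1/4) = 5.4%, and 0.054 × 27 is about 1.5 patients. One death classed differently turns 22/27 into 21/27.

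**Step 8: could the interval serve as a test?** A lower 95% limit of at least 80% would need 26/27, which happens with probability 23% even at a true 90%. The interval is therefore useful for reporting, not as a pass mark.

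**The case against.** The strongest reply is that the plan sets no pass/fail rule. The endpoint speaks of developing and refining strategies. Section 11.3.2 uses the rates and cascade graphics to find the steps with most attrition, interviews also feed the adaptations, and Section 11.3.1 looks to the later state trial for reaching the goals. Nothing in the protocol turns on 21 against 22 of 27. The list of descriptive statistics is also open-ended, so intervals are not excluded. All of this stands, and it limits the point to reporting and interpretation. It does not remove it: an endpoint phrased as meeting goals needs some statement of precision, and none is planned.

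Several stronger readings are tempting but unsupported.
- A reader might infer that both goals rest on 27 patients. Only patient retention does.
- A reader might infer that strategies well below the goal often meet it, or that strategies well above it often fail. For pooled retention the chance of meeting it is 14% at ten points below and 5% at fifteen; at a true 90% it is missed 5% of the time. The uncertainty matters near the goal.
- A reader might infer that one lucky cycle could carry the endpoint. The plan does not say that each cycle is judged separately against the goals, and the post-pilot revision is openly preparation for the next trial.
- A reader might take Section 8.6 to turn deaths into losses to follow-up. That section addresses patients who withdraw or do not respond, while Section 10.2.3.2 and Appendix 10 capture death separately. What is missing is one line on how a known death counts in the rate.

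**Conclusion.** The concern holds as a matter of precision and reporting. Rates that form part of a primary endpoint are set against fixed goals with no measure of uncertainty. For patient retention the result that just reaches 80% carries an exact interval of 62% to 94%. Under the implied rule, a true 75% reaches the goal 30% of the time, a true 70% does so 14% of the time, and a true 85% misses it 21% of the time. For patient recruitment the size cannot be fixed without the number telephoned; at an assumed 45 the interval is 44% to 74%.

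These figures assume independent patients, with no clustering by clinic or provider, and read a goal as met when the observed rate is at least the goal. The single-cycle figures also assume the cycle sizes.

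Two further inferences go too far. The primary endpoint need not be rewritten: enrolment is closed, and intervals can be added without touching it. Nor does this finding set a sample-size rule for the statewide trial, which lies outside this protocol.

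**What to change.** In Section 11.3.2:
1. Report each recruitment and retention rate, for patients and healthcare workers, overall and per adaptation cycle, with its numerator, denominator and exact (Clopper-Pearson) 95% interval.
2. Base any statement that a goal was met on the rate together with its interval, not on the point estimate alone.
3. Report known deaths before month 3 separately from loss to follow-up.

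This needs a few lines of analysis and no new data. The price is a less clear-cut feasibility conclusion.
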